## Home Based Virtual Rehabilitation for upper extremity

**Title of Project:**

**Principal Investigator:**

**[name] PT PhD**

**Funding Source(s):**

**NIDILRR #90RE5021-01-00**

**NIH NICHD #1R15HD095403-01A1**

### 1. Purpose/Specific Aims

The overarching aim of this study is to provide a mechanism for patients to engage in progressive motor practice for a meaningful time period. We aim to improve on the positive outcomes found in our work on patients in the chronic phase and the pilot work being done on patients in the acute in-patient phase post stroke to determine whether we can further improve functional recovery using a home based system.

Aim 1: Evaluate compliance with Home-Based Virtually Simulated hand/arm gaming activities and two computer game groups, one with motivation enhanced (ME) simulations and one with non-enhanced (MnE) versions, as compared to compliance with Standard hand/arm home Exercises (HBSE). Hypothesis: Participants in the ME and MnE group will show significant compliance as compared to the control group (HBSE) and the ME group will be superior to the MnE group.

Primary Outcome Measures: For the HBVS group, 1) time on task will be measured by the daily computer file time stamp and 2) amount of moving time will be measured by the actual movement time recorded by the games. For the computer games groups 1) time on task will be measured by recording start and stop time of practice in a notebook and 2) amount of moving time will be measured by commercially available activity monitors.

Aim 2: Evaluate the effectiveness of home-based virtually simulated hand/arm gaming activities (HBVS) for individuals with stroke as compared to a program of standard hand/arm home exercises (HBSE). Hypothesis: Participants completing HBVS training will exhibit significantly improved clinical, kinematic and neurophysiological outcomes as compared to the control group (HBSE).

Primary Outcome Measures for Aim 2: Wolf Motor Function Test, Upper Extremity Fugl-Meyer Assessment of Sensorimotor Recovery after Stroke, Action Research Arm Test, Perception of System Questionnaire, the Stroke Impact Scale, Kinematics, Cortical mapping.

Aim 3: Evaluate the impact of the motivation enhancements designed into computer games to provide a more enjoyable training experience. Hypothesis: Enjoyment of the games will be a more valid predictor of compliance than personal factors.

Primary Outcome Measures for Aim 3: The Intrinsic Motivation Inventory, The Patient Activation Measure, qualitative data collected during semi-structured interviews.

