### ***3.3 Sample Size Justification***

In this pilot study we will seek sufficient power to detect a clinically significant difference in the Wolf score changes in these two pre-planned, primary comparisons. To evaluate these effects of training, we will assume a power level of .8 and a significance level of 0.05. With presumed correlation among repeated measures of 0.1 and effect size of 0.3, we will need a sample size of 25 subjects in each of the three groups (HBVS, ME and MnE) to observe a significant effect for the first comparison (G\*Power, version 3.1.5). Although we will screen for patients with homogeneous impairments, by its nature stroke is an extremely variable condition. Due to possible subject attrition, we will use a total of 30 subjects in each of the two groups.

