### **5. Data Handling and Statistical Analysis**

All efforts will be made to keep subjects' personal information confidential. All subject names will be removed from the data and the data will be tagged using a coded ID number.

Demographic, clinical outcome and survey data will first be recorded on paper. All kinematic and computerized performance data will be collected on computer. These computer files will be identified by the coded subject ID number. All data will be transferred to an Excel spreadsheet with subjects identified by this same ID number. Spreadsheets will be stored on a drive that is password protected. Data will only be accessible to study staff and will be retained for seven years. The link between subject identity and subject ID number will be destroyed when data collection is completed.

Our primary outcome measures will be the WMFT (Aim 2) and the duration of motor activity (measure of compliance, Aim 1). The primary outcome measures and all secondary outcome measures described above will be subjected to a repeated measured analysis of variance, with between-group factors Therapy Type (Virtual Simulations (VS), Standard Exercise (SE)) and within-group factor Test (Before, Post, One Month retention, Six Months Retention). Our post-hoc analyses of the Therapy Type by Test interaction effects will focus on the Month 1 versus Month 6 comparison. We will be quantifying training effects by comparing group means as well as by percent change in performance, and by comparing the recovery curves obtained from Tests 1-4. All clinical outcomes used are well established measures of upper extremity functional recovery with published minimum clinically important differences which we will use to evaluate the significance of our findings.

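### Aim 1 predicts three arm contrasts on compliance, but no visible text orders, gates or adjusts them, and the written two-level ANOVA cannot test them

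*Protocol*

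**What the plan says.** **Hypothesis.** Protocol Section 1, Aim 1, says that the ME and MnE participants "will show significant compliance as compared to the control group (HBSE) and the ME group will be superior to the MnE group". This compares each game group with standard exercise and the two game groups with each other.

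**Measures.** The same section lists two primary measures for Aim 1. For the HBVS group the wording is "1) time on task will be measured by the daily computer file time stamp and 2) amount of moving time will be measured" from the games' own records; notebook and activity-monitor versions are given for the computer game groups. Section 5 lists only one: "Our primary outcome measures will be the WMFT (Aim 2) and the duration of motor activity (measure of compliance, Aim 1").

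**Model.** Section 5 puts the primary outcomes through a repeated-measures ANOVA. Its between-group factor has two levels, virtual simulations and standard exercise. The only post-hoc focus named is the one-month against the six-month retention test.

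**Significance level.** It appears once, in Section 3.3: "we will assume a power level of .8 and a significance level of 0.05". The purpose given there is to "detect a clinically significant difference in the Wolf score changes in these two pre-planned, primary comparisons". Sidedness is not stated, and no level is given for Aim 1.

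**SAP.** It describes a two-arm study (enhanced vs unenhanced games) with the Intrinsic Motivation Inventory as primary. Adherence enters through a regression of total time on that inventory. The visible text has no arm contrast on compliance.

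**The concern.** Compliance is one of the two outcomes that Section 5 calls primary, and Aim 1 attaches three separate predictions to it. They support different conclusions: that games beat standard exercise, that only enhanced games do, or that the enhancement itself matters. The visible text does not say which contrast decides Aim 1, whether all must succeed, or in what order they are tested.

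The one model written down does not settle this. A two-level factor pools ME and MnE, so it cannot compare them with each other or compare either one separately with HBSE. Whoever analyses Aim 1 must add tests that the plan does not specify. They could choose the deciding contrast, and on the Section 1 text the deciding measure, after seeing the data. If the added tests are unadjusted pairwise comparisons, the chance of some false compliance finding is well above the level of a single test.

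**Working it through.** **1. The plan's own figure.** Section 3.3 states: "With presumed correlation among repeated measures of 0.1 and effect size of 0.3", and "we will need a sample size of 25 subjects in each of the three groups (HBVS, ME and MnE"). Take the effect size as Cohen's f and use the between-groups test of a repeated-measures ANOVA with k groups, m measurements and N subjects in total:

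λ = f² · N · m / (1 + (m − 1)ρ), on k − 1 and N − k degrees of freedom.

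- k = 2, m = 2, N = 50: λ = 0.09 × 50 × 2 / 1.1 = 8.18, power 0.800. This gives exactly 25 per group.
- k = 3: the same test needs 21 per group with m = 2, or 13 with m = 4.

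The stated size is therefore reproduced by a two-group comparison. It gives no support for a three-arm analysis of compliance. The documents state no family-wise error rate to reproduce.

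**2. Number of tests.** Three contrasts on one measure (Section 5) make 3 tests. Three contrasts on two measures (Section 1) make 6. If the tests were independent, the family-wise rate would be 1 − 0.95³ = 14.3% or 1 − 0.95⁶ = 26.5%. The contrasts share arms, so the true rates are lower and need simulation.

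**3. Simulation under the global null.** Assumptions: three arms of 25, one normal value per subject per measure, equal variances, the same measurement in every arm, and correlation r between the two measures. For arms i and j,

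t = (mean_i − mean_j) / √[ ((s_i² + s_j²)/2) · (2/n) ], on 2n − 2 = 48 degrees of freedom.

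The gate is F = n × (variance of the three arm means) / (mean within-arm variance), on 2 and 3n − 3 = 72 degrees of freedom, applied to each measure separately. There were 100,000 trials per row. The Monte Carlo standard error near 12% is √(0.12 × 0.88 / 100,000) = 0.1 percentage point.

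| r | Any two-sided rejection, 1 measure | Same, 2 measures | Predicted direction only, 1 measure | Same, 2 measures | After F-gate, 1 measure | Same, 2 measures |
|---|---|---|---|---|---|---|
| 0 | 12.26% | 23.03% | 6.65% | 12.78% | 4.98% | 9.75% |
| 0.3 | 12.08% | 22.40% | 6.49% | 12.26% | 5.01% | 9.62% |
| 0.5 | 11.96% | 21.16% | 6.40% | 11.54% | 4.89% | 9.11% |
| 0.7 | 12.27% | 19.54% | 6.64% | 10.65% | 5.02% | 8.43% |
| 0.9 | 12.19% | 16.77% | 6.52% | 9.10% | 4.97% | 7.16% |
| 0.999 | 12.28% | 12.69% | 6.68% | 6.94% | 4.91% | 5.13% |

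The one-measure columns do not depend on r; their spread is simulation noise. Arm size matters little: at r = 0.5 the first two rates are 11.97% and 21.21% with 30 per arm, and 12.39% and 21.64% with 10 per arm.

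**4. Relative size.** One measure, any direction: 12/5 = 2.4 times the single-test rate. Two measures: 12.69/5 = 2.5 to 23.03/5 = 4.6 times. Predicted direction, one measure: 6.5/2.5 = 2.6 times. If all three contrasts had to succeed, the rate under the global null would be about 0%.

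**The case against.** The strongest objection is that these rates belong to an analysis the plan does not contain. Section 5 writes an ANOVA with two levels and no pairwise arm tests, and the 0.05 in Section 3.3 is tied to Wolf score changes. A reader might infer that the plan itself carries a false-positive rate above 20% for compliance. The documents do not support that: it needs the two measures of Section 1 rather than the one in Section 5, an assumed correlation, and tests that the reader supplies. This part of the objection stands, so every rate here is conditional.

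Three further points stand in part.

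- **Direction.** The hypothesis is directional, and on one measure false claims in the predicted direction occur about 6.5% of the time. The matching rate for a single test is 2.5%, so the inflation remains.
- **Reading of the hypothesis.** If all three contrasts were required, or if a three-arm F-test came first, there would be no inflation on one measure. Neither rule is written.
- **Arms and instruments.** Section 3.3 names HBVS, ME and MnE without HBSE, then speaks of two groups. Section 1 gives different instruments to different groups and none to HBSE. The simulation assumes a common measurement in all three arms.

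A reader might also infer that multiplicity is handled nowhere. The SAP refers to a Table 5 of planned comparisons that is not in the supplied text, so the absence can be asserted only for what is visible. Table 5 belongs to a two-arm design and may not cover contrasts with HBSE.

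The objection does not rescue the plan. A model that cannot contain the predicted contrasts cannot protect them, and it leaves the choice of contrast open. The pilot label in Section 3.3 does not remove this, because Aim 1 predicts significant differences on an outcome called primary.

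**Conclusion.** The point holds in conditional form. Aim 1 makes three arm predictions; Sections 1 and 5 disagree on whether there are two primary compliance measures or one; the written two-level factor cannot test the predictions; and no order, gate or adjustment is visible. If each contrast is tested at two-sided 0.05, the family-wise error with no arm differences is about 12% on the single measure of Section 5. On the two measures of Section 1 it is about 13-23%. The 0.05 is borrowed from the Wolf calculation, and the correlation between measures is an assumption shown over its range. The one-measure figure is the firmer one, because it needs no correlation. The lasting defect is that the contrast deciding Aim 1 has not been fixed in advance.

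**What to change.** 1. Reconcile Protocol Sections 1, 3.3 and 5 on the arms and on the compliance measures, and state which of them the SAP's two-arm design covers.
2. Make duration of motor activity the sole Aim 1 primary, as Section 5 already suggests, and time on task secondary. This matters for the gate: applied separately to two primary measures, it would still allow up to about 9.75%.
3. For compliance, replace the two-level Therapy Type factor with a three-level arm factor (ME, MnE, HBSE). Test it with one overall F-test at 0.05, and test the pairwise contrasts at two-sided 0.05 only if it is significant. With exactly three arms this holds the family-wise rate at 5%: once one arm differs, at most one pairwise null can still be true.
4. Alternatively, pre-specify a fixed order, for example ME vs HBSE, then MnE vs HBSE, then ME vs MnE, each at 0.05, stopping at the first non-significant result.
5. State the significance level and sidedness for Aim 1.

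The cost is protocol and SAP wording, with no extra participants for error control. The small downside is that a pairwise difference cannot be claimed when the gate or an earlier step fails. Bonferroni would also control the rate, but it would need 0.05/3 = 0.0167 per test for three tests, or 0.05/6 = 0.0083 for six.

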## **4. Study Variables**

### ***4.1 Independent Variables or Interventions***

The two **computer game groups, Motivation Enhanced (ME) and Motivation Non-Enhanced (MnE)** will use the NJIT- Home Virtual Rehabilitation System (HoVRS) to play a series of computer games developed to practice movement of the hand and fingers. Subjects will first come into our lab, perform pre-tests as well as a pre-intervention training session. Then a physical therapist and engineer will set up the apparatus in subject's home and will train them on how to use the system and play the games in their home during the first week. The physical therapist and engineer will be in contact with subjects throughout the training and will visit subjects' homes as needed if problems are encountered. Additionally, the system allows the therapist to remotely monitor each day's activity.

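### The Aim 1 compliance instruments are assigned to groups in a way that conflicts with the SAP, and games versus HBSE has no stated common instrument

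*Protocol*

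**What the plan says.** **Protocol, section 1 (Aim 1).** The hypothesis is that "Participants in the ME and MnE group will show significant compliance as compared to the control group (HBSE"), and that ME will be superior to MnE. Two outcomes are listed, time on task and moving time, and instruments are given for two labels:

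- HBVS: "For the HBVS group, 1) time on task will be measured by the daily computer file time stamp", and "amount of moving time will be measured by the actual movement time recorded by the games".
- Computer games groups: "For the computer games groups 1) time on task will be measured by recording start and stop time of practice in a notebook", and "amount of moving time will be measured by commercially available activity monitors".

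No instrument is given for HBSE.

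**Protocol, other sections.**

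- Section 4.1 describes the two "computer game groups, Motivation Enhanced (ME) and Motivation Non-Enhanced (MnE") as users of HoVRS and adds that "the system allows the therapist to remotely monitor" each day's activity. Section 4.1.1 says HoVRS has a server-based logging and reporting component.
- The software text for the video exercise group describes an interface listing the exercises. It does not mention recording of exercise time.
- Section 4.2 lists duration of motor activity among the data from daily gaming, as an item separate from game duration.
- Section 5 makes duration of motor activity the Aim 1 primary outcome and analyses it by therapy type, virtual simulations versus standard exercise.
- Section 3.3 counts "25 subjects in each of the three groups (HBVS, ME and MnE"), a set of groups that does not include HBSE.

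**SAP.** Both groups (enhanced and un-enhanced) use HoVRS. Table 4 has the system record intervention days, total time and average daily time. The Aim 2 outcome text gives the reason: patients' own reports of exercise time run high. The SAP text available describes no HBSE arm.

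**The concern.** Compliance in the games arms against HBSE is one of the two Aim 1 hypotheses, and section 5 puts an Aim 1 primary outcome on that contrast. A compliance difference can be read as an effect of the intervention only if minutes are counted the same way in each arm. If the counting method follows the arm, any net difference between methods is added to the arm difference, and recruiting more subjects does not remove it.

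There is also a practical problem. Staff who follow section 1 to the letter would collect notebooks from arms whose practice the system can log, and would have no instruction at all for HBSE. Practice time that was not captured during training cannot be recovered afterwards.

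**Working it through.** The plan gives no figure for this point, so the check is a comparison of the texts, followed by a simple illustration.

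**Step 1. Who are the computer games groups?** By section 4.1 they are ME and MnE on HoVRS. HBVS appears in section 3.3 as a third group beside them, but section 4.1 describes only the two game groups and a video exercise group. So the HBVS label in section 1 may be a separate arm or a name for game training in general. The text does not settle this.

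**Step 2. Does the notebook sentence fit the rest?** For time on task it conflicts directly with the SAP, which uses system times in both game groups because self-report overestimates. For moving time the SAP has no counterpart, but protocol section 4.2 draws duration of motor activity from the games, not from a monitor. Sections 4.1 and 4.1.1 show that logging exists. They do not say that compliance is scored from the logs.

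**Step 3. The two readings.**

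| | Slip for HBSE | Literal |
|---|---|---|
| Time on task, games | file time stamp | notebook (ME, MnE) |
| Time on task, HBSE | notebook | not stated |
| Moving time, games | recorded by the games | activity monitor (ME, MnE) |
| Moving time, HBSE | activity monitor | not stated |
| Games versus HBSE | instrument confounded with arm | HBSE source missing |
| ME versus MnE | same instruments | same instruments |

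Neither reading states a common instrument for games versus HBSE.

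**Step 4. Which construct carries the primary?** Section 4.2 separates duration of motor activity from game duration, so the section 5 primary most naturally corresponds to moving time. On the slip reading it would then compare game-recorded with monitor-recorded movement. Neither is self-report, so the SAP's warning does not give a direction for that comparison.

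**Step 5. Illustration on the slip reading.** The inputs g, h, f and r are all assumptions; the documents give no error size for any instrument.

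*Time on task.* Let g be the true games advantage, h the overstatement by time stamps and f the overstatement by notebook:

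observed games/HBSE ratio = (1 + g)(1 + h)/(1 + f)

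With h and f each between 0 and 0.20:

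- g = 0: from 1.00/1.20 = 0.833 (-16.7%) to 1.20/1.00 = 1.20 (+20%).
- g = 0.20: from 1.20 × 1.00/1.20 = 1.00 (0%) to 1.20 × 1.20/1.00 = 1.44 (+44%).
- h = f: no distortion.

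*Moving time.* If the monitor records r minutes per game-recorded minute, equal movement appears as 1/r:

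- r = 0.80: 1/0.80 = 1.25 (+25%).
- r = 1.25: 1/1.25 = 0.80 (-20%).

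I give no false-positive rate. The documents give no variance for compliance, and the group sizes in section 3.3 come from a Wolf-score calculation that does not name HBSE.

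**The case against.** The strongest reply is that the sentence is an obvious labelling slip in a self-described pilot, that the other Aim 1 hypothesis (ME versus MnE) is untouched, and that the SAP may have dropped HBSE altogether. Much of this stands. The slip is the likelier reading, ME versus MnE shares instruments either way, and the mismatch in arms between protocol and SAP is the larger problem, of which this is one symptom. But correcting the label leaves instrument tied to arm, and the protocol still plans the HBSE contrast.

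Three stronger readings are tempting, and the documents do not support them:

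- *A reader might infer that no common compliance measure exists.* Section 5 names one, duration of motor activity, and section 1 uses the same two constructs throughout. What is missing is a common instrument or data source.
- *A reader might infer that the notebook contradicts the device description.* A notebook kept alongside system logging would be compatible with sections 4.1 and 4.1.1. The conflict is with the SAP's choice of source.
- *A reader might infer that the HBSE contrast is invalid, or biased in a known direction.* On the literal reading HBSE might use the same notebook and monitors, which would give ME and MnE versus HBSE shared instruments; the text does not say. Inclusion of duration of motor activity in the gaming data does not exclude another source for HBSE. Self-report inflation in HBSE would tend to hide a games advantage in time on task, but time stamps can also overstate practice and notebook entries can be missed.

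**Conclusion.** The point holds as an inconsistency and an omission, and should be fixed. Section 1 conflicts with the SAP on how adherence is recorded in the game groups, and no HBSE instrument is stated for a contrast that the protocol still plans on an Aim 1 primary outcome. On the likelier reading, instrument is confounded with arm for games versus HBSE. The sign and size of the resulting bias are unknown; the ranges above show only what assumed errors would do. On the literal reading, self-report is used where system logs are available and the HBSE source is missing. ME versus MnE is not confounded on either reading.

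The view that moving time is the section 5 primary is an inference from section 4.2, not something the protocol states.

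**What to change.** 1. Correct the group labels in the Aim 1 outcome text. Reconcile them with protocol sections 3.3, 4.1, 4.2 and 5 and with the SAP's treatment protocol, Table 4 and Aim 2, and state whether the HBSE contrast is still planned.
2. Use HoVRS system logs for adherence in every game arm, as the SAP does for its two groups.
3. If the HBSE contrast is kept, state the HBSE data source. Base the between-arm comparison on one instrument used in every arm: the same activity monitor for moving time, or the same time-on-task method. Use HoVRS logs in the game arms as a check.
4. Do not test game-recorded against monitor-recorded moving time as if they were one measure. Keep in-game movement time for comparisons among game arms.

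**Cost.** Items 1 and 2 are text changes. Item 3 falls away if the HBSE contrast is dropped. If it is kept, a common monitor may need extra equipment, and whether the video interface can log sessions has to be checked. Item 4 is a text change with a real consequence: without a common monitor, the HBSE contrast on what is probably the section 5 Aim 1 primary can only be descriptive, or must move to time on task. Time on task has its own limits. A common notebook keeps self-report error, and video time stamps show that the program was in use, not that the arm moved.

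### The protocol does not say which arms form the Aim 2 treated group: HBVS is a separate group in Sections 1 and 3.3, is absent from Section 4.1, and is not mapped to the VS level in Section 5

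*Protocol*

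**What the plan says.** - **Protocol Section 1, Aim 1.** The aim is to "Evaluate compliance with Home-Based Virtually Simulated hand/arm gaming activities and two computer game groups" (ME and MnE), against HBSE. The hypothesis under it names only ME, MnE and HBSE, and expects ME to be superior to MnE. The compliance measures differ by label: "For the HBVS group, 1) time on task will be measured by the daily computer file time stamp", with moving time taken from the games, while the computer game groups use a notebook and activity monitors. HBSE is given no measure.
- **Protocol Section 1, Aim 2.** The aim is to "Evaluate the effectiveness of home-based virtually simulated hand/arm gaming activities (HBVS) for individuals with stroke as compared to a program" of standard home exercise (HBSE). The hypothesis is that "Participants completing HBVS training will exhibit significantly improved clinical, kinematic and neurophysiological outcomes as compared to the control group (HBSE").
- **Protocol Section 3.3.** For the first comparison on the Wolf score it requires "25 subjects in each of the three groups (HBVS, ME and MnE"), with power 0.8, significance level 0.05, correlation 0.1 and effect size 0.3. HBSE is not in the list. The section mentions two primary comparisons without defining them, and ends by planning 30 subjects in each of two groups.
- **Protocol Section 4.1.** It describes the two "computer game groups, Motivation Enhanced (ME) and Motivation Non-Enhanced (MnE"), both on the HoVRS system, and a video home exercise group. It describes no other intervention.
- **Protocol Section 5.** The Wolf Motor Function Test (WMFT, Aim 2) and duration of motor activity (Aim 1) are primary. Both go into a repeated-measures analysis of variance with "between-group factors Therapy Type (Virtual Simulations (VS), Standard Exercise (SE")) and four test occasions.
- **SAP, Research Design and Methods and the Aim 1 Subjects paragraph.** Two arms, enhanced and unenhanced, both on HoVRS; 30 subjects; no standard exercise arm.

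**The concern.** These are conflicting statements about who is in the trial's comparison groups, not a missing detail. In one place HBVS is a group of its own with its own measurement rule. In another, no one is described as receiving it. The analysis section then uses a third label, VS, and leaves its membership open.

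Two things are at stake. First, the treated side of the main efficacy comparison has no fixed definition, so its size, its standard error and what it estimates are not settled in advance. Second, a factor with only VS and SE as levels has no term for ME against MnE, so the analysis written for the Aim 1 primary outcome cannot test half of the Aim 1 hypothesis.

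**Working it through.** **1. Sections side by side**

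| Place | Groups on the game side | Control |
|---|---|---|
| Section 1, Aim 1 objective | HBVS, ME, MnE | HBSE |
| Section 1, Aim 1 hypothesis | ME, MnE | HBSE |
| Section 1, Aim 2 | HBVS | HBSE |
| Section 3.3, group list | HBVS, ME, MnE | none listed |
| Section 3.3, last sentence | two groups, not named | |
| Section 4.1 | ME, MnE | video home exercise |
| Section 5 | VS | SE |
| SAP | enhanced, unenhanced | no exercise arm |

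No single set of arms fits every row.

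**2. Reproducing the 25 per group**

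Inputs from Section 3.3: effect size 0.3, read as Cohen's f (the G\*Power scale for analysis of variance), so d = 2 × 0.3 = 0.6; ρ = 0.1; α = 0.05; power 0.80. The number of groups k, the number of measurements m and the test family are not stated.

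For the between-group test, λ = f²·N·m / [1 + (m − 1)ρ], with k − 1 and N − k degrees of freedom. With k = 2, m = 2 and N = 50:

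λ = 0.09 × 50 × 2 / 1.1 = 8.18, on 1 and 48 df, power **0.800**.

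This returns exactly 25 per group. The other repeated-measures variants tried (k = 2 to 4; m = 2 to 4; between, within or interaction) return 8 to 21 per group. A one-way analysis returns 45, 37 or 32 for k = 2, 3 or 4. So the figure matches two equal groups measured twice; k = 2 and m = 2 are inferred from that match.

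**3. The same inputs with VS as ME and MnE pooled**

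The SD of the mean of two measurements is √(1.1/2) = 0.742, so the standardised difference is 0.6/0.742 = 0.809. The t-test noncentrality is 0.809 × √[n₁n₂/(n₁ + n₂)].

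| VS vs SE | √[n₁n₂/(n₁ + n₂)] | Noncentrality | Power |
|---|---|---|---|
| 25 vs 25 | 3.536 | 2.86 | 0.800 |
| 50 vs 25 | 4.082 | 3.30 | 0.903 |
| 30 vs 30 | 3.873 | 3.13 | 0.869 |
| 60 vs 30 | 4.472 | 3.62 | 0.947 |

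The last row applies only if there are three arms of 30, that is 90 subjects. Two groups of 30 make 60.

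Standard error ratio, pooled to single arm: √[(1/50 + 1/25)/(1/25 + 1/25)] = √0.75 = 0.866, or 13% smaller. This ratio depends only on group sizes, not on the inferred m. The absolute powers do depend on m: with four measurements, as in Section 5, they are 0.954 (25 vs 25) and 0.989 (50 vs 25).

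**4. When the estimate changes**

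With equal arm sizes, the pooled effect is the mean of the two arm effects. Suppose ME has d = 0.6 against HBSE, and let MnE vary (an assumption; the documents give no values):

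| MnE effect | Pooled effect | Power, 50 vs 25 |
|---|---|---|
| 0.6 | 0.60 | 0.903 |
| 0.3 | 0.45 | 0.686 |
| 0 | 0.30 | 0.371 |

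If the two versions work equally well on the WMFT, only precision and power change.

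**The case against.** The strongest reply is that the intended design is easy to guess. HBVS in the Section 3.3 list may be a slip for HBSE; correcting it gives exactly the three arms of Section 4.1. Aim 2 describes HBVS in general terms that fit both game arms, and the Aim 1 hypothesis names only ME, MnE and HBSE. On that view VS is plainly ME plus MnE.

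Much of this stands. Pooling is the most workable reading, and a stand-alone HBVS arm has no intervention behind it. But the slip is inferred. Correcting it would not remove the separate HBVS measurement rule in Section 1, explain the two groups at the end of Section 3.3, or define VS in Section 5.

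Three stronger readings are tempting and are not supported:

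- **That the trial is underpowered either way.** A single-measurement t test at d = 0.6 gives 0.547 (25 vs 25) and 0.676 (50 vs 25). That test discards the correlation of 0.1 that Section 3.3 states alongside the effect size. On the inputs that return 25 per group, power is at least 0.80 under both readings at the planned effect.
- **That the choice of reading necessarily changes the effect estimate.** The protocol predicts a difference between ME and MnE on compliance, not on the WMFT. The SAP's Aim 3 predicts one on the Action Research Arm Test, but the WMFT is not among the measures in SAP Table 4.
- **That the plan invites testing ME alone or MnE alone as the Aim 2 treatment.** No section names either arm by itself in that role.

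**Conclusion.** The contradiction is real and affects the primary efficacy comparison. Sections 1, 3.3, 4.1 and 5 cannot all be followed, and the SAP does not resolve them because it describes a different two-arm study. Section 5's two-level factor also leaves the ME against MnE part of Aim 1 untested.

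The size is moderate. Moving from one VS arm to pooled arms raises power from 0.800 to 0.903 at 25 per arm, and from 0.869 to 0.947 at 30 per arm if three arms of 30 exist; the standard error falls by 13%. If VS is simply one of two groups of 30, the pooled reading brings no extra subjects. The power figures rest on reading 0.3 as Cohen's f and on two measurements, both inferred. A shift in the estimate depends on a WMFT difference between ME and MnE that would have to be assumed.

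**What to change.** Protocol:

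1. Define the arms once as ME, MnE and HBSE, and use those labels throughout. State in Aim 2, Section 3.3 and Section 5 that HBVS and VS mean all subjects randomised to ME or MnE, and that SE means HBSE. Remove HBVS as an extra group from Aim 1 and Section 3.3.
2. In Section 5, fit group as a three-level factor. Pre-specify (ME + MnE)/2 − HBSE as the Aim 2 contrast and ME − MnE for Aim 1. Report each game arm against HBSE as supportive. With 25 per arm the Aim 2 contrast has variance factor ¼(1/25 + 1/25) + 1/25 = 0.06, the same as 50 against 25, so the three-level model loses essentially nothing.
3. In Section 3.3, correct the group list and the closing sentence on two groups. Restate power for the chosen contrast, the actual number of arms and the number of measurements used. The total should agree with Section 3.5.3, where 300 approached at 15–20% yields 45 to 60 eligible, fewer than three arms of 25 (75) or 30 (90).
4. In Section 1, assign the system time-stamp and game-recorded measures to ME and MnE, and the notebook and activity-monitor measures to HBSE.

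SAP: reconcile it with the protocol, either by adding the standard exercise arm and the Aim 2 contrast or by stating that it covers only the ME against MnE part, and explain how its 30 subjects relate to the protocol's total.

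Cost: wording changes in Sections 1, 3.3 and 5 and in the SAP, plus one rerun of the power calculation. The definition itself needs no new data or subjects. The small downside is that the Aim 2 effect becomes an average over two game versions. If the sponsor intends a different Aim 2 contrast, stating it once in the same places would also resolve the conflict.
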